## **Project summary**

The project aims to construct and evaluate a prototype system that enables military pilots to train under conditions of orthostatic hypotension and ischemic hypoxia. Both of these phenomena are experienced by aircraft crews of mainly highly manoeuvrable aircraft, and their syndromes include loss of colour vision, loss of peripheral vision, blackout and finally G-induced loss of consciousness (G-LOC). A motorised tilt table to generate orthostatic (ORTHO) stress combined with an automatically controlled lower body negative pressure (LBNP) chamber to extort pooling of blood in the lower extremities will be developed in order to obtain new knowledge on counteracting the above-mentioned effects and minimising the risk of their occurrence. This will help optimise the selection procedures of candidates with the best physiological predispositions to work as military pilots. The system will be equipped with modules for monitoring biomedical parameters of a subject, including cerebral oxygenation, which will ensure their safety and provide a source of data for performing advanced analyses. The ORTHO-LBNP system will be subjected to comprehensive laboratory tests. After a successful testing, a research protocol will be developed and a pilot study will be carried out involving pilots and/or cadets of the Polish Air Force Academy. It is anticipated that new indicators will be proposed as a result of the pilot study to enable an objective assessment of the predispositions to pursue a military pilot career. The prototype system developed within the project will also be easily adaptable to the needs of clinical and sports medicine as well as rehabilitation. As an output of the project realisation, the ORTHO-LBNP system will be developed at technology readiness level 9 and presented to the scientific community in the form of a series of papers that will report on the results of the system designing phase and the pilot study.

## **General information**

### ***Protocol Title***

Evaluation of a prototype system for generating conditions of orthostatic hypotension and blood pooling in the lower body

### ***Short title***

Evaluation of the ORTHO-LBNP system

### ***Acronym***

ORTHO-LBNP

## Rationale & background information

A number of cardiovascular disorders are observed when human body is subjected to accelerations other than the gravity of Earth. Although the first consideration on the medical aspects of the influence of the variable gravitational field date back to 1818 [1], only the rapid development of human centrifuges, tilt tables and under- or overpressure chambers in the 1960s allowed for controlling the gravitational stimuli quantitatively [2]-[5]. Accelerations directed from head to feet ( $+G_z$ ) and accelerations acting oppositely ( $-G_z$ ) have been of particular interest to space and aviation medicine. In the first case, blood moves toward the lower extremities and its drain from the brain may cause oxygen deficiency leading in sequence to greyout, tunnel vision, blackout, and G-induced loss of consciousness (G-LOC) [6]. The adverse symptoms of  $+G_z$  acceleration are additionally intensified if the positive stimulus is preceded by  $-G_z$  acceleration, i.e., a push-pull effect occurs [7]. The literature explains this increased regulatory response through the significant contribution of sympathetic activity [8]. A list of states deviating from the Earthly gravity is complemented by weightlessness and microgravity, i.e., zero- and near zero-gravity states, respectively. These aspects are mainly researched in the context of space missions during which, promptly upon entering weightlessness, blood shifts toward the head [9]. The cardiovascular system adapts to the new conditions after a time [10], however blood content in the lower part of the body remains unnaturally low and long-term stay in space impairs vestibulo-cardiovascular reflex [11] and leads to, e.g., a change in heart shape and loss of heart muscle mass [12]. Returns from space missions are also aggressive for the body due to symptoms accompanying them, such as orthostatic intolerance, hypotension, dizziness, and syncope [13]. For the above-mentioned reasons, methods for increasing the body tolerance to  $+G_z$  and  $-G_z$  accelerations and for counteracting the disadvantageous effects of weightlessness are of fundamental meaning in space and aviation medicine.

In general, three methods for real or simulated changing direction and value of the gravity field vector are used:

- centrifugation,
- head up tilt (HUT) and head down tilt (HDT) tests,
- lower body negative pressure (LBNP) and lower body positive pressure (LBPP) tests.

Modern human centrifuges enable for mapping acceleration profiles that reflect flight conditions with great accuracy, and the pilot is subjected to real accelerations. Although the centrifuge is recognised as the best flight simulator, high costs of its construction, operation and maintenance have resulted in searching for alternatives. One of them is a tilt table. This device of modest complexity offers a generation of stimuli in the range of -1 g (tilt of  $-90^\circ$ , HDT) to 1 g (tilt of  $+90^\circ$ , HUT) in the  $G_z$  axis. Despite this limitation, even weak stimuli below 1 g in the  $G_z$  axis ( $+1 G_z$ , in short) trigger a series of reflex reactions whose monitoring allows for assessing the efficiency of the cardiovascular regulatory mechanisms. On the other hand, placing the lower body of the pilot (usually from the waist area down) in an underpressure chamber simulates cardiovascular effects corresponding to stimuli greater than  $+1 G_z$ . Some authors report on supine LBNP at -50 mmHg (millimetre of mercury), which induced the hemodynamic response similar to that observed at an acceleration value of  $+2 G_z$  [14]. To simulate  $+2 G_z$  heart rate (HR) effects in weightlessness, an increase in LBNP to -90 mmHg is required [15]. Other authors attempt to prove that the LBNP test can be a more effective and practical stimulus than centrifugation [16].

The underpressure chamber is often placed on the tilt table in order to strengthen the  $+G_z$  stimulus by using LBNP and moving the pilot from supine to vertical position simultaneously. Moreover, this configuration allows for achieving the push-pull effect when the LBNP and/or HUT exposures are preceded by a HDT try. Similarly to the HDT test, the LBPP technique aims to reverse or prevent the effects of orthostatic hypotension. It is however much less commonly used, mainly due to problems met when designing one device purposed for generating positive and negative pressures.

The Military Institute of Aviation Medicine is the only institution in Poland, where candidates for military aviation are verified for their physiological predispositions. They have to meet two main criteria to get the highest health category that predisposes them for training on highly manoeuvrable aircraft. One of them is to obtain the right result of medical and psychological tests, whereas the other criterion is to withstand a linearly increasing acceleration ( $0.1 G_z/s$ ) up to a value of  $+5.7 G_z$ , generated by the human centrifuge available at the institute. In order to verify the possibility of performing selection procedures with a limited outlay, we have developed the ORTHO-LBNP system, i.e., a prototype device consisting of the tilt table to generate orthostatic stress and the underpressure chamber to extort pooling of blood in the lower extremities, as during  $+G_z$  accelerations. Although typical values of LBNP do not descent below  $-100$  mmHg, i.e., it would be difficult to achieve of effects corresponding to an acceleration greater than  $+4 G_z$ , a properly matched tilt and LBNP profiles can generate physiological disorders at a level sufficient to evaluate the subject's resistance to accelerations or to develop the ability to adapt variable gravitational stimuli.

## Study goals and objectives

The objectives of the pilot study can be summarised as follows:

1. Testing the prototype device with participation of humans, where the result measures relate both to feasibility and health outcomes.
2. Checking the system dynamics and verifying how faithfully the system maps the pre-programmed tilt and LBNP profiles.
3. Verifying the signal quality and analysing changes in basic physiological parameters when applying a sequence of the pre-programmed tilt and LBNP profiles.
4. Verifying if new indicators can be proposed for an objectivised assessment of the physiological predispositions of candidates for military aviation.

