## Research scenarios

### Scenario I

[figure not shown]
Scenario I will be composed of seven phases, shown in Fig. 6, which can be characterised as: (1) 300-s check before the stimuli, (2) LBNP is applied stepwise with 11.1 mmHg/15 s decrement to -100 mmHg, and then this value is sustained for 120 s, (3) 180-second phase of rest between stimuli, (4) 75°-HUT (5°/s) for 120 s after a 15-s reversing of the gravity vector (-30°), (5) 180-second phase of rest between stimuli, (6) 75°-HUT (5°/s) accompanied by an exposure to an LBNP of -60 mmHg increased linearly by -4 mmHg/s, and then this value is sustained for 120 s during HUT, and (7) 120-s check after the stimuli.

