**Fig. 6. Tilt and LBNP profiles in 24-min Scenario I.**

### Scenario II

Scenario II will be composed of seven phases, shown in Fig. 7, which can be characterised as: (1) 120-s check before the stimuli, (2) 75°-HUT (45°/s) for 60 s after a 3-s reversing of the gravity vector (-30°), (3) 180-second phase of rest between stimuli, (4) LBNP decreases linearly by -20 mmHg/s to -100 mmHg, and then this value is sustained for 60 s, (5) 180-second phase of rest between stimuli, (6) push-pull, i.e.,  $3 \times 75^\circ$ -HUT (45°/s) preceded by -30°-HDT (45°/s) and accompanied by an exposure to an LBNP of -60 mmHg decreased linearly by -20 mmHg/s, and then this value is sustained for 30 s during HUT, and (7) 120-s check after the stimuli.

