**Fig. 7. Tilt and LBNP profiles in 16-min Scenario II.**

The pilot study will be carried out in an isolated room in the presence of a physician (physiologist), a paramedic and an ORTHO-LBNP system operator. The paramedic will prepare the subject for the study by placing on his/her body electrodes and measuring sensors that will be removed after completion of the study. The subject will be asked to close his/her eyes during the tests and to place his/her hands on the rest. In order to cause the least disturbance, no conversation will be held with the subject. Only if disturbing symptoms will occur, will the subject immediately report this to the personnel. The physician will systematically be observing the subject's cardiogram, his/her HR, CNAP wave, and systolic and diastolic blood pressure (SBP and DBP, respectively) in comparison with the changing tilt of the table and negative pressure in the chamber. Any time, at the request of the subject or on the instruction of the doctor, the operator will interrupt the tests. The tilt table then will return to the Trendelenburg position if interruption occur during HUT and/or LBNP stimuli, or horizontal position if interruption occur during HDT stimulus. At the same time atmospheric pressure will be resumed in the chamber.

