## Expected Outcomes of the Study

During the implementation of both research scenarios, all signals/parameters that can be acquired by the medical monitoring subsystem will be recorded. However, in scenario I the main emphasis will be placed on the analysis of basic physiological parameters, i.e., HR, inter-beat interval (IBI), SBP, DBP, mean arterial pressure (MAP), stroke volume (SV), cardiac output (CO), left ventricular ejection time (LVET), rate pressure product (RPP), and total peripheral resistance (TPR), calculated using the ECG and CNAP signals. The latest literature shows that the analysis of basic physiological parameters, e.g., heart rhythm and blood pressure, enables for predicting orthostatic hypotension [23] and reveals precursory signs of syncope [24]. Our intention is to verify the behaviour of a group of cadets experiencing accelerations on a regular basis who are subject to tests in a device of a novel design. We expect that a stronger stimulus will cause greater changes in the values of the analysed physiological parameters. Among the stimuli used, the strongest one should be HUT accompanied by LBNP. The analysis should indicate these physiological parameters that should be taken into account in the development of an orthostatic tolerance index (OTI).

The results of scenario II will be focused not only on the impact of the stimuli, but will also be analysed in terms of the distinguishing of subjects with different level of flight experience and quantifying an examined person's propensity to endure gravitational stimuli. Both analysis of basic physiological parameters as well as analysis of indices determining the level of oxygenation of brain areas acquired with the in-house-designed NIRS module will be

performed. It is expected that greater changes in brain oxygenation indices will be seen in the subjects without flight experience than in active pilots that have undergone a training improving their G-tolerance.

We anticipate that new indicators will be proposed to enable an objective assessment of the predispositions to pursue a military pilot career. Finally, this should make the selection procedures in military aviation easier.

At least two manuscripts, one containing the results of scenario I, the other containing the results of scenario II, will be submitted for publication.

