## **Dissemination of Results and Publication Policy**

The results will be first reported via the National Centre of Research and Development, Poland, to the Ministry of National Defence, Poland. The Ministry will decide whether to implement the ORTHO-LBNP system into the selection process of candidates for military pilots.

The publications will be prepared under the leadership of the PI. The PI decides on the author lists. Only persons who gave the conception of the prototype system, modelled the tilt table and LBNP chamber, designed and constructed the prototype system, coordinated certification procedures, programmed the tilt and LBNP profiles, designed the experimental protocol, coordinated the pilot study, processed data for analysis, analysed and verified data, and interpreted the results, can be included on the author lists. The person who contributes the most to the preparation of the manuscript will be its first author. If the PI is not the author of the largest contribution, he will be acknowledged as the last author of the article.

All authors will review the manuscripts and accept their final version.

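### The plan aims to quantify each person's propensity to endure gravitational stimuli but defines no individual tolerance outcome, so it can show responsiveness and a difference by flight experience, not individual predisposition

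*Combined protocol and SAP*

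**What the plan says.** **Aim.** Objective 4 (Study goals and objectives) is "Verifying if new indicators can be proposed for an objectivised assessment of the physiological predispositions of candidates for military aviation". Expected Outcomes of the Study is more ambitious. Scenario I is to point to the parameters that should enter an orthostatic tolerance index, and Scenario II is directed at "quantifying an examined person's propensity to endure gravitational stimuli". Under Dissemination of Results and Publication Policy, "The Ministry will decide whether to implement the ORTHO-LBNP system into the selection process of candidates for military pilots".

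**Stimuli.** Every phase is pre-programmed. In Scenario I, for example, the stepwise LBNP reaches its lowest value "and then this value is sustained for 120 s, (3) 180-second phase of rest between stimuli". In Scenario II, "LBNP decreases linearly by -20 mmHg/s to -100 mmHg, and then this value is sustained for 60 s". The text after Fig. 7 adds: "Any time, at the request of the subject or on the instruction of the doctor, the operator will interrupt the tests". Safety Considerations says what happens to the table and chamber if presyncope appears.

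**Analysis.** The Statistical Analysis Plan gives phase means, standard deviations and standard errors, changes from phase 1 and, in Scenario II, a comparison of subjects with and without flight experience. It covers 10 parameters in Scenario I and 17 in Scenario II.

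**Existing criterion.** The Rationale describes how candidates for highly manoeuvrable aircraft are judged now. Besides medical and psychological tests, "the other criterion is to withstand a linearly increasing acceleration" of 0.1 Gz/s up to +5.7 Gz, "generated by the human centrifuge available at the institute". Neither Study Design nor the Statistical Analysis Plan mentions it.

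**The concern.** An indicator of predisposition has to separate people who tolerate the load better from people who tolerate it worse. For that, each subject's response must be set against some measure of that subject's tolerance, and the plan provides none. A parameter that moves strongly under HUT or LBNP has been shown to respond to the stimulus. Whether a large rise in heart rate or peripheral resistance reflects good compensation or little reserve cannot be read from the size of the change.

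The results go to the Ministry, and the protocol describes no validation step in between. Parameters could therefore reach a selection decision under the name of predisposition or tolerance when the study has shown only that they react, or that they differ between trained and untrained groups.

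**Working it through.** The plan states no sample-size, power or precision figure for this aim, so there is none to reproduce. The check is a reading of the sections side by side, followed by two calculations on stated assumptions.

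**1. Does the design yield an individual tolerance value?**
- Scenario I holds each stimulus for 120 s. Scenario II holds for 60 s, and for 30 s in each push-pull cycle. No phase is extended until a limit is reached, so a subject who completes has no tolerance value.
- A subject who does not complete gives a crude one: stopped, in a given phase, at a given time. The Statistical Analysis Plan does not name interruption, presyncope or time to either as an outcome.
- The centrifuge criterion appears only as background.
- Count: up to 20 subjects in Scenario I plus up to 30 in Scenario II makes up to 50. For 0 of them is a response compared with a tolerance value.

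**2. What can Scenario I show?** It has one group, all with flight experience. Expected Outcomes links a greater change to a stronger stimulus, not to a better or worse subject. Without a comparator or a tolerance outcome, the result is responsiveness only.

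**3. What can the Scenario II contrast show?** Let g = 1 for experienced and 0 for inexperienced subjects, t a person's predisposition (mean 0, SD 1, the same distribution in both groups), and y the indicator:

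y = -0.8 g + ρ t + √(1 - ρ²) e, with e standard normal.

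The -0.8 SD is an assumed training effect. Within each group the variance of y is ρ² + (1 - ρ²) = 1, and the expected group difference is -0.8 + ρ × 0 = -0.8, whatever ρ is. A simulation of 15 v 15 with 4,000 runs per setting agrees:

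| ρ (indicator with predisposition) | Mean group difference | Mann-Whitney power |
|---|---|---|
| -0.6 | -0.80 | 0.52 |
| 0 | -0.80 | 0.52 |
| +0.6 | -0.80 | 0.52 |

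If experience acts through training, the contrast looks the same whether a larger value marks a better, an equal or a worse candidate. If prior selection also shifts t by δ between groups, the difference becomes -0.8 + ρδ. Training and selection are then added together in one number and cannot be separated.

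**4. What could a link to centrifuge records add?** Assume that records exist, that they vary between subjects, and that the correlation is r = 0.5. With Fisher's z, z = atanh(0.5) = 0.549, SE = 1/√(n - 3), and the interval is tanh(z ± 1.96 SE):
- Scenario I, n = 20: 0.549 ± 1.96/√17 = 0.549 ± 0.475, giving 0.07 to 0.77.
- Scenario II flight-experienced subjects, n = 15: 0.549 ± 1.96/√12 = 0.549 ± 0.566, giving -0.02 to 0.81.

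These are Pearson intervals. Those for a rank correlation are slightly wider.

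**The case against.** **This is a pilot study.** Objective 4 is the last of four and asks only whether indicators can be proposed. Proposing candidates for later validation is a normal pilot aim, and the index is described as something still to be developed. This stands: lack of validation does not contradict objective 4. It does not cover the individual-level aim in Expected Outcomes or the selection decision that follows.

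**Scenario II does give a direction.** Expected Outcomes predicts greater changes in brain oxygenation in subjects without flight experience than in pilots whose training has improved their G-tolerance. A reader might infer from the missing tolerance outcome that the trial can say nothing about direction. The documents do not support that. If flight experience is accepted as a proxy, this known-groups comparison gives a group-level direction, stated in advance for one family of variables. But the protocol itself attributes it to training. It may also reflect prior selection and age: the range is 18 to 30 overall, with school students set against graduates or near-graduates. It does not reach individual predisposition.

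**Interruption is possible.** So it is not true that no tolerance information could arise. It is simply not defined or analysed as an outcome.

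**No selection rule is given.** A reader might also infer that Scenario I will choose index parameters by size of change. Expected Outcomes says only that the analysis should point to them.

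**Conclusion.** The point holds as a limit on what may be concluded. As written, Scenario I supports statements about responsiveness and Scenario II statements about flight experience. Neither supports a statement about a person's predisposition, because for none of up to 50 subjects is a response compared with individual tolerance. This should be settled before results are reported, but it does not undermine the feasibility, profile-fidelity or signal-quality objectives.

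It is tempting to pool the flight-experienced subjects of both scenarios (20 + 15 = 35), where the interval would be 0.20 to 0.71, and to conclude that centrifuge records would settle direction. The documents do not support this. The stimuli differ: LBNP in steps of 11.1 mmHg per 15 s against 20 mmHg/s, tilt at 5°/s against 45°/s, and holds of 120 s against 30 to 60 s. A subject's change is therefore not the same variable in the two scenarios. The usable sizes are 20 and 15, and at 15 the interval includes zero.

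The contrast result assumes a 0.8 SD training effect and equal predisposition in the two groups. The intervals assume r = 0.5 and full recruitment. The documents give no effect size and do not say that each cadet has a centrifuge record. Restriction to people already selected would weaken any correlation.

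**What to change.** In the Statistical Analysis Plan and Expected Outcomes:

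1. **Limit the claim.** Report a parameter selected on size of change only as 'responsive to the stimulus', and one selected on the Scenario II contrast only as 'differs by flight experience'. Call it an indicator of predisposition only if it is associated with an individual tolerance measure. State this limit in the report to the Ministry.
2. **Use the tolerance information the study already generates.** Record interruption or presyncope, as it arises under the existing stopping procedures, as an outcome in every subject: yes or no, phase, time, and whether the subject or the physician prompted it. Describe each candidate parameter's change against it, using a time window that all compared subjects completed. This also covers the students. The stopping procedures are unchanged.
3. **Add centrifuge results where they help.** With consent, and only where records exist and vary between subjects, give a descriptive rank correlation within each scenario (n up to 20 and up to 15, not pooled), labelled exploratory because 10 and 17 parameters are examined. If all subjects reached +5.7 Gz, the highest level is constant and the correlation is undefined. Heart rate at a common G level is no substitute, since it can be read either way like the parameters themselves.

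**Cost.** Item 1 is wording. Item 2 is a few data fields and a descriptive table. Item 3 is a consent line and record retrieval. Interruptions may be few, records may be missing or at ceiling, and the claim made to the Ministry becomes more modest.
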